9.3.6.2 Estimand Strategy for Continuous Endpoints

The population level summary will be the difference in mean change (or percentage change) from baseline to the endpoint of interest between delgocitinib cream and alitretinoin capsules.

The change (or percentage change) from baseline to the endpoint of interest will be analysed using an analysis of covariance (ANCOVA) model with effects of treatment group, region, hyperkeratotic/non-hyperkeratotic subtype, and baseline value (of the measure of interest).

When analyses require multiple imputation (MI) procedures of data, 100 complete datasets will be sampled. For each dataset, the ANCOVA model will be fitted. The estimates and standard errors from the analyses will be combined using Rubin's rule to provide the estimate and associated standard error.

Primary Estimand: 'Composite' Strategy

For the primary analysis, observed and missing data will be handled according to the IEs, as described in Table 9-2.

For the sensitivity analysis, which is rather conservative against the delgocitinib group, missing data at the endpoint of interest, for participants who did not experience IEs prior to that, will be handled as follows:

- For participants in the delgocitinib cream group, missing data will be imputed as WOCF (including baseline value).
- For participants in the alitretinoin capsules group, missing data will be imputed using MI assuming MAR.

First Supplementary Estimand: 'Pandemic Modified Composite' Strategy

Observed and missing data will be handled according to the IE, as described in Table 9-2.

All missing or 'treated as missing' data will be imputed using MI assuming MAR within treatment groups. The WOCF imputation of relevant data points not affected by the COVID-19 pandemic will be applied.

Second Supplementary Estimand: 'Treatment Policy' Strategy

Observed data and missing data will be handled according to the IEs, as described in Table 9-2.

Missing data at Week 12 and Week 24, independent of the COVID-19 pandemic, will be imputed using MI assuming MAR within 4 groups defined according to treatment group and whether the participant has experienced an IE (independent of the COVID-19 pandemic). For imputation purposes, data available from all participants will be used.

For the endpoint of interest, missing data or 'treated as missing' data due to the COVID-19 pandemic will be imputed using MI assuming MAR within treatment group using data from participants who have not experienced an IE.

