9.3.6 Estimand Strategy

9.3.6.1 General Considerations

The analysis of endpoints related to efficacy and health-related quality of life will be based on the FAS.

The following primary and supplementary estimands will be defined for binary, continuous, and AUC endpoints (primary and key secondary endpoints):

- The primary estimand will use a 'composite' strategy to handle IEs. With a 'composite' strategy, the occurrence of an IEs is a component of the endpoint. The occurrence of any IE will lead to assume failure of the randomised treatment. For continuous endpoints, observed data after the IEs will be imputed as non-response by using WOCF (including baseline value) which is considered an extremely unfavourable value.
- A first supplementary estimand will use a 'pandemic modified composite' strategy. The strategy follows a 'composite' strategy for IEs independent of the COVID-19 pandemic. However, data collected after the IE related to the COVID-19 pandemic will be 'treated as missing' and imputed assuming MAR.
- A second supplementary estimand will use a 'treatment policy' strategy which attempts to quantify the effect of the randomised treatment, ignoring the occurrence of IEs. This policy reflects the intention-to-treat (ITT) principle and is intended to measure the effectiveness of the treatment under conditions closer to 'real world' conditions where patients will not adhere perfectly to the protocol when taking medication. Data collected for the endpoint of interest are used regardless of whether an IE occurred, except for the occurrence permanent discontinuation of IMP related to the COVID-19 pandemic data which will be assumed MAR and imputed.

To support the 'treatment policy' strategy, participants who experience IEs prior to Week 12 will be asked to attend the primary endpoint visit at Week 12 and nominal visit at Week 24 for collection of data. Participants who experience IEs between Week 12 and Week 24 will be asked to attend the nominal visit at Week 24 for collection of data.

For primary and key secondary endpoints only, pre-specified sensitivity analyses will also be conducted for selected combinations of endpoints and estimands to assess the robustness of the results with respect to the handling of missing data.

Analysis to summarise and assess the effect of patterns of missing data related to the COVID-19 pandemic will be specified in the SAP prior to DBL.

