Missing data at Week 12 and Week 24 independent of the COVID-19 pandemic will be imputed using MI assuming MAR within 4 groups defined according to treatment group and whether the participant has experienced an IE (independent of the COVID-19 pandemic).

Missing data or 'treated as missing' data at Week 12 and Week 24 due to the COVID-19 pandemic will be imputed using MI assuming MAR within treatment group using data from participants who have not experienced an IE.

For the sensitivity analysis, missing data at Week 12 and Week 24 will be imputed as non-response, unless data is missing or 'treated as missing' due to the COVID-19 pandemic in which case it will be imputed using MI assuming MAR within treatment group using data from participants who have not experienced an IE.

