10.5 Appendix 5: COVID-19 Pandemic Contingency Plan

Without compromising the safety of participants and trial integrity, it is expected that efforts are made to secure attendance at sites for all visits, ensuring important efficacy and safety assessments for the trial

If on-site visits are not possible due to local authority-issued preventive measures, the affected site will postpone screening and randomisation of new participants until on-site visits can be conducted. For already randomised participants, post-baseline visits can be done remotely via phone or video. At phone/video visits, no investigator assessments of efficacy can be done, but the following data will be collected remotely, according to the SoA (Table 1-1):

- AE reporting.
- Treatment compliance (daily completion in the eDiary).
- Concomitant medication and concurrent procedures.
- HESD (daily completion in the eDiary).
- Participant assessment of local tolerability (weekly completion in the eDiary).
- PROs (DLQI, HEIS, EQ-5D-5L, TSQM, WPAI-CHE, PGI-S, and PGI-C). The participants will receive a link to complete the PROs in a web browser from their own device.
- New CHE lesions.
- Urine pregnancy test. Women of childbearing potential will receive 1 extra urine pregnancy test at the randomisation visit to keep at home in case on-site visits become impossible during the trial. The participant will perform the test at home and inform the investigator about the result via phone and to send a picture of the test to the site or show it via video. Additional urine pregnancy tests can be shipped to the participant's home together with IMP (see below) if needed.
- For participants treated with alitretinoin:
 - Serum cholesterol and serum triglycerides (fasting values) should continue to be monitored by a local laboratory, at the timepoints outlined in the SoA (Table 1-1).
 - Remote consultation to allow for adequate monitoring of mental health should be maintained at the timepoints outlined in the SoA (Table 1-1). The potential for psychiatric disorders may be increased by COVID-19 isolation measures and this may complicate the clinical picture.

In the eCRF, it will be recorded whether a visit or a given assessment was done remotely or not done. If not done, it will be recorded if this was due to the COVID-19 pandemic.

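### Under treatment policy, values missed because of COVID-19 are imputed only from participants without an intercurrent event, with no exception for those already rescued or off drug for other reasons

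*Combined protocol and SAP*

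**What the plan says.** The second supplementary estimand follows a treatment-policy strategy. Section 9.3.6.1 describes it so: "Data collected for the endpoint of interest are used regardless of whether an IE occurred". The one exception named there is permanent discontinuation of trial drug related to COVID-19, after which values are assumed missing at random and imputed. Rescue and non-COVID discontinuation are not excepted.

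Section 9.3.6.2 then gives two imputation rules, chosen by the cause of missingness:

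- Missing independently of COVID-19: multiple imputation "within 4 groups defined according to treatment group and whether the participant has experienced an IE".
- Missing or treated as missing because of COVID-19: values affected by the "COVID-19 pandemic will be imputed using MI assuming MAR within treatment group using data from participants who have not experienced an IE".

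Section 9.3.6.4 has the same pair of rules for AUC endpoints. Section 9.3.6.3 has it for binary endpoints, where values affected by the "pandemic will be imputed using MI assuming MAR within treatment group using data from participants who have not experienced an IE". The binary sensitivity analysis under treatment policy sets missing values to non-response, but sends COVID-related ones to the no-IE donors.

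Section 9.3.2 records COVID-related missingness visit by visit, separately from the IE. For remote visits, Appendix 5 states: "At phone/video visits, no investigator assessments of efficacy can be done".

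**The concern.** Imputing by treatment and IE status suits a treatment-policy estimand, because a participant who has been rescued or is off drug is represented by others in the same position. The COVID rule drops that principle whenever the reason for the missing value is the pandemic. Yet the reason a visit was missed does not change what had already happened to the participant.

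The case can arise. After permanent discontinuation, participants leave the regular visit schedule. Apart from the early-termination and safety follow-up visits, they return only at Week 12 (if they stopped before it) and Week 24 (Sections 4.1 and 7.1). Those return visits exist to support this estimand. If one is held by phone, no HECSI or IGA-CHE score is obtained, and few post-IE efficacy values remain to offset an unsuitable donor set.

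The primary estimand counts every IE as failure. Treatment policy is one of the analyses showing what happens when IEs are ignored, so its imputation should respect what is known about IEs.

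**Working it through.** **The plan's own figure.** Section 9.5 assumes a difference of 7.5, SD 30, 1-sided 2.5% and 80% power.

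- n per arm = 2 × (1.960 + 0.842)² × 30² / 7.5² = 251.2, so 252 per arm and 504 in total, against 510 stated.
- With 255 per arm, SE = 30 × √(2/255) = 2.657, and power = Φ(7.5/2.657 − 1.960) = 80.6%.

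The sample size reproduces and is not in dispute.

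**The texts side by side.** Take a participant rescued at Week 6 whose Week 12 visit is held by phone because of COVID-19, so that HECSI is missing.

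| Place | What applies to this value |
|---|---|
| 9.3.6.1 | IEs are ignored; only COVID-related discontinuation is excepted, so this participant is not |
| Table 9-2 | Row for missing after rescue: multiple imputation under MAR, no donor set named, no split by COVID cause |
| Table 9-3 | COVID-related: imputed within treatment group, no restriction to no-IE participants |
| 9.3.6.2 (same in 9.3.6.3 and 9.3.6.4) | Donors are no-IE participants in the same treatment group |
| 9.3.6.2, had the visit been missed for another reason | Donors are participants in the same treatment-by-IE group |

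Three donor sets can be read from the plan for one value: no-IE only (text), the whole arm (Table 9-3), or the participant's own IE group (if Table 9-2 is taken to mean that IE status decides first). In the binary sensitivity analysis the same participant is a non-responder if the visit was missed for another reason, but may be imputed as a responder if the reason was COVID-19.

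**Size.** None of the following is in the documents; all are assumptions:

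- e, share of an arm with rescue or non-COVID discontinuation: 10-30% (alitretinoin), 10% (delgocitinib)
- c, share of those whose endpoint value is missing because of COVID-19: 1-10%
- D, mean HECSI gap between participants with and without an IE: 15-30 points, worse after an IE

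Shift in one arm's mean = e × c × D. Shift in the between-arm difference = (e_ali − e_del) × c × D.

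- One arm, lowest: 0.10 × 0.01 × 15 = 0.015. Highest: 0.30 × 0.10 × 30 = 0.90, which is 255 × 0.30 × 0.10 = about 7.7 participants.
- Between arms:

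| e (alitretinoin / delgocitinib) | c | D | Shift | Share of 7.5 |
|---|---|---|---|---|
| 10% / 10% | any | any | 0 | 0% |
| 30% / 10% | 1% | 15 | 0.03 | 0.4% |
| 20% / 10% | 5% | 30 | 0.15 | 2% |
| 30% / 10% | 10% | 15 | 0.30 | 4% |
| 30% / 10% | 10% | 30 | 0.60 | 8% |

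The largest cell was checked by simulation: 1,500 trials, 255 per arm, SD 30, no-IE mean changes of −32.5 and −40, with missing values replaced by the donor-group mean. The treatment difference was −12.92 under the literal rule, −13.53 when imputing by IE status, and −13.50 with complete data. The 0.6-point shift is confirmed. Against the standard error it is 0.60/2.657 = about 0.2.

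**The case against.** The best counter-argument is Table 9-2. The treatment-policy paragraph in Section 9.3.6.2 opens by referring to it, and the table sorts by IE first. It splits missing values by COVID cause only for participants without an IE. The first supplementary estimand follows the same order. On this view the no-IE donor rule was meant only for participants with no IE or with COVID-related discontinuation, and the four-group rule for everyone else. That may well be the intention, but the table does not settle it: it names no donor set, Table 9-3 splits by cause of missingness, and the text states its rule without exception. Section 9 also calls itself a summary and leaves technical detail to the SAP, but no separate SAP text on donor sets appears in the documents reviewed.

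Three stronger inferences are tempting and are not supported.

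- A reader might take "For imputation purposes, data available from all participants will be used" to cancel the four groups, so that everyone missing after an IE is imputed from pooled donors (for example 5-10% of an arm × 30 points = 1.5-3.0 points). The sentence directly follows the four-group rule. Its natural meaning is that participants with and without IEs contribute, each within their own group; the other reading empties the four-group rule of content. Its absence from the binary section therefore does not show that HECSI change and HECSI-90 use different donors. In the composite sensitivity analysis, Section 9.3.6.3 derives response after imputing the underlying score, which points to a single HECSI imputation.
- A reader might say that the participant is imputed as if still on drug. As if no IE had occurred is more exact: by Week 24 the no-IE set includes participants who stopped at IGA-CHE 0 or 1 under the protocol. Imputation variables are not listed, so the participant's own poor earlier scores may also soften the effect.
- A reader might extend the point to COVID-related discontinuation. That handling is deliberate and disclosed in Sections 9.3.2 and 9.3.6.1 and Table 9-2, and is not challenged.

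**Conclusion.** The point holds as a gap between the stated imputation rule and the estimand it serves. It concerns only COVID-missed values after rescue or non-COVID discontinuation, in the treatment-policy analyses of continuous, binary and AUC endpoints and in the binary sensitivity analysis.

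The expected effect is small: about 0-0.6 HECSI points between arms. This rests wholly on the assumed rates and gap; effective rescue treatment would narrow D and reduce it further. If alitretinoin has more IEs, the literal rule shrinks delgocitinib's apparent advantage; if delgocitinib has more, it enlarges it.

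Nothing here touches the trial's main conclusion. Sections 9.3.7 and 9.3.8 base the confirmatory tests on the composite estimand. The change is still worth making, because the wording admits more than one donor set and choosing among them after seeing the data would weaken a supporting analysis.

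**What to change.** In the treatment-policy paragraphs of Sections 9.3.6.2, 9.3.6.3 and 9.3.6.4:

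1. Limit the no-IE donor rule to participants who, before the visit being imputed, had no IE or only a COVID-related discontinuation.
2. Impute any value missing after rescue or non-COVID discontinuation, whatever the reason for the missed visit, within the treatment-by-IE group.
3. In the binary sensitivity analysis, treat a value missing after rescue or non-COVID discontinuation as non-response, as for other missing values.
4. Align Tables 9-2 and 9-3 with these rules and name the donor set in each.
5. Keep the sentence on using data from all participants; at most, add that this applies within each group.

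The cost is a few sentences and one changed condition in the imputation code. No new data are needed, because IEs and COVID-related missingness are already recorded. Section 9 allows a revised SAP before database lock.

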9.3.6.3 Estimand Strategy for Binary Endpoints

The population level summary will be the difference in response rates between delgocitinib cream and alitretinoin capsules.

The difference in response rates between the 2 treatment groups with the 95% CI will be calculated using the Cochran-Mantel-Haenszel (CMH) test stratified by region and hyperkeratotic/non-hyperkeratotic subtype.

When analyses require MI procedures of data, 100 complete datasets will be sampled. For each dataset, the difference in response rates will be analysed using the CMH test stratified by region and hyperkeratotic/non-hyperkeratotic subtype. The results of the analyses will be combined using Rubin's rule to provide the estimated treatment difference and associated standard error, and the 95% CI for the treatment difference will be calculated.

Primary Estimand: 'Composite' Strategy

For the primary analysis, observed data and missing data will be handled according to the IEs, as described in Table 9-2.

For the sensitivity analysis, which is rather conservative against the delgocitinib group, missing data at the endpoint of interest for participants who did not experience IEs prior to that will be handled as follows:

- For participants in the delgocitinib cream group, missing data will be imputed as non-response.
- For participants in the alitretinoin capsules group, missing data will be imputed using MI (100 iterations) assuming MAR. Binary response/non-response will be determined after imputation of the original raw continuous values when binary variable is obtained by derivation (e.g. for the HECSI-90 from baseline up to Week 24, the percentage of reduction from baseline will be derived from imputed values).

First Supplementary Estimand: 'Pandemic Modified Composite' Strategy

Observed data and missing data will be handled according to the IEs, as described in Table 9-2.

All missing or 'treated as missing' data will be imputed using MI assuming MAR within treatment groups. Once the 100 complete data sets have been generated by MI, non-responder imputation of relevant data points not affected by the COVID-19 pandemic will be applied.

Second Supplementary Estimand: 'Treatment Policy' Strategy

For the primary analysis, observed data and missing data will be handled according to the IEs, as described in Table 9-2.

Missing data at Week 12 and Week 24 independent of the COVID-19 pandemic will be imputed using MI assuming MAR within 4 groups defined according to treatment group and whether the participant has experienced an IE (independent of the COVID-19 pandemic).

Missing data or 'treated as missing' data at Week 12 and Week 24 due to the COVID-19 pandemic will be imputed using MI assuming MAR within treatment group using data from participants who have not experienced an IE.

For the sensitivity analysis, missing data at Week 12 and Week 24 will be imputed as non-response, unless data is missing or 'treated as missing' due to the COVID-19 pandemic in which case it will be imputed using MI assuming MAR within treatment group using data from participants who have not experienced an IE.

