1.3 Schedule of Activities (SoA)

Table 1-1 Schedule of Activities (SoA)

	6										Follow-	D	Primary	Nominal	Unscheduled	Protocol
	Screen- ing			Tre	atme	nt pe	riod			EOT/ ET ¹	up ²	Pregnancy follow-up ³	endpoint visit at Week 12, it	Week 24 visit, if applicabl	visit, if applicable ⁵	section
Visit	1	2	3	4	5	6	7	8	9	10	11	12	applicable ⁴	e ⁴		
Week	-4 to -1	0	1	2	4	8	12	16	20	24	2 weeks	5 weeks				
Day	-28 ⁶ to -7	1	8	15	29	57	85	113	141	169	after last dose	after last dose				
Visit window (days)	-	-	±3	±3	±3	±3	±3	±3	±3	±3	±3	+6				
Eligibility / baseline assessme	Eligibility / baseline assessments															
Informed consent(s)	X															10.1.3
Participant eligibility	X	X														5.1, 5.2
Demographics	X															8
Fitzpatrick skin type	X															8, Table 8-1
Medical history (including CHE treatment history)	X															8
Classification of CHE (including patch test ⁷)	X														(X) ⁷	8, Table 8-2
Height		X														8
Weight	X	X														8
Treatments and randomisati	on															
Randomisation		X														6.3
Instruction for use of IMP		X														6.2.1
Dispensing of IMP		X			X	X	(X)	(X)	(X)						(X)	6.1
Determination of affected area(s)		X													(X)	6.2.1
New CHE lesions			X	X	X	X	X	X	X	X			X	X	X	6.2.1

	G										E-II	D	Primary	Nominal Wook 24	Unscheduled	Protocol
	Screen- ing			Tre	atme	nt pe	riod			EOT/ ET ¹	Follow- up ²	Pregnancy follow-up ³	endpoint visit at Week 12, if	Week 24 visit, if applicabl	visit, if applicable ⁵	section
Visit	1	2	3	4	5	6	7	8	9	10	11	12	applicable ⁴	e ⁴		
Week	-4 to -1	0	1	2	4	8	12	16	20	24	2 weeks	5 weeks				
Day	-28 ⁶ to -7	1	8	15	29	57	85	113	141	169	after last dose	after last dose				
Visit window (days)	-	-	±3	±3	±3	±3	±3	±3	±3	±3	±3	+6				
Delgocitinib cream topical application		Twice-daily for 16 weeks							Stop/re s nece							6.2.1.1
Alitretinoin capsules oral administration		Once	e-dail	y for 1	12 we	eks			p/resta ecessa							6.2.1.2
Treatment compliance (eDiary)			Daily ⁸													6.4
Return of treatment and accountability					X	X	X	(X)	(X)	(X)					(X)	6.4
Concomitant medication and concurrent procedures	X	X	X	X	X	X	X	X	X	X	X		X	X	X	6.8
Blinded assessor assessment	of efficacy															
HECSI		X	X	X	X	X	X	X	X	X			X	X	(X)	8.1.1
IGA-CHE	X	X	X	X	X	X	X	X	X	X			X	X	(X)	8.1.2
Participant assessments of ef	ficacy at h	ome														
eDiary handout/training 8	X															8.1.3.1
HESD					Da	ily 8							Daily ⁸	Daily 8		8.1.3.1

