9.3 Statistical Analyses

9.3.1 General Considerations

Significance tests will be 1-sided using the 2.5% significance level. All confidence intervals will be presented with 95% degree of confidence, unless otherwise specified.

An observed-cases approach will be used for tabulations of data by visit (that is, involving only those participants who attended each specific visit).

Categorical data will be summarised using the number and percentage of participants in each category. Continuous data will be summarised using the mean, median, SD, 1st quartile, 3rd quartile, minimum, and maximum values.

Baseline measurements will be defined as the latest available observation at or prior to the date of randomisation.

The statistical analyses were performed using SAS software (SAS Institute, Cary NC), version 9.3 or later.

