9.5 Sample Size Determination

Approximately 510 participants will be randomly assigned to trial treatment in a 1:1 ratio, with 255 evaluable participants per treatment group. Approximately 660 participants will be screened to achieve this target.

With 510 participants randomised, the trial will provide 80% power to establish superiority of delgocitinib cream with regard to change from baseline to Week 12 in HECSI based on a 1-sided hypothesis test at a 2.5% significance level, assuming a difference in the mean change from baseline to Week 12 in HECSI of 7.5 (with a standard deviation of 30) between the 2 treatment arms (Ruzicka et al, 2008). Since there is limited published data on alitretinoin in terms of HECSI, anticipated treatment difference between delgocitinib and alitretinoin has been set using IGA scales as a surrogate endpoint (LP0133-1273 trial). Expected standard deviation is based on data observed in LP0133-1273 trial.

10 Supporting Documentation and Operational Considerations

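### HECSI-90 and IGA-CHE TS at Week 12 could use baseline HECSI through a standardised risk difference: an optional gain in precision, probably small and possibly nil

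*Combined protocol and SAP*

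**What the plan says.** Section 9.3.6.3 defines the binary estimand's summary: "The population level summary will be the difference in response rates between delgocitinib cream and alitretinoin capsules". The difference and its 95% CI are "calculated using the Cochran-Mantel-Haenszel (CMH) test stratified by region and hyperkeratotic/non-hyperkeratotic subtype". These two factors are the randomisation strata (Section 4.1). No baseline severity term is included.

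The continuous endpoints are handled differently. In Section 9.3.6.2 the ANCOVA covariates are treatment group, region, subtype "and baseline value (of the measure of interest"). For the HECSI change endpoints that baseline is HECSI; for itch and pain it is the participant's own HESD score.

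Section 9.3.6.4 lists a baseline value among the covariates of the robust ANCOVA for AUC endpoints, and gives AUC of HECSI-90 as an example of such an endpoint. Its later paragraph on multiply imputed data leaves the baseline term out of the list. The section does not say which baseline is meant for AUC of HECSI-90; baseline HECSI is the natural reading.

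Baseline HECSI is available. In the Schedule of Activities it is scheduled at Visit 2 under "Blinded assessor assessment of efficacy".

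Under Section 9.1.1, HECSI-90 and IGA-CHE TS at Week 12 are the first and second key secondary tests in a fixed sequence that ends at the first non-significant result.

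**The concern.** A baseline covariate that predicts response can sharpen the estimated difference in response rates at no cost in data. The plan accepts this for the HECSI change endpoints, and lists a baseline covariate for HECSI-90 accumulated over time, but not for HECSI-90 at Week 12. It gives no reason for the difference.

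The argument is stronger for IGA-CHE TS. Every participant must enter at IGA-CHE 4 (inclusion criterion 3), so baseline IGA-CHE carries no information. HECSI also scores the extent of lesions and runs from 0 to 360, so it can still vary among participants all graded severe. Success means reaching 0 or 1 whatever the starting extent, so an association is plausible. For HECSI-90 the argument is weaker, because the endpoint is already a percentage of the participant's own baseline.

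At stake is the chance of passing the first two key secondary tests. The documents state no power for either.

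**Working it through.** **Inputs from the documents.** "Significance tests will be 1-sided using the 2.5% significance level" (Section 9.3.1). Section 9.5: "Approximately 510 participants will be randomly assigned to trial treatment in a 1:1 ratio, with 255 evaluable participants per treatment group"; "the trial will provide 80% power to establish superiority of delgocitinib cream"; "assuming a difference in the mean change from baseline to Week 12 in HECSI of 7.5 (with a standard deviation of 30").

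**Inputs that are assumptions.** Response rates, and the strength of association between baseline HECSI and response. Neither is in the documents.

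**1. The plan's own figure.** Per arm, n = 2 × 30² × (1.960 + 0.842)² / 7.5² = 251.2, so 252 per arm and 504 in total, against the stated 255 and 510. Power at 255 per arm is Φ(7.5 / (30 × √(2/255)) − 1.960) = 80.6%. The stated figure reproduces. It concerns the continuous primary endpoint and is unaffected by this point.

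**2. Binary endpoint without baseline adjustment.** Assume 18% versus 28%. The SE of the risk difference is √((0.18 × 0.82 + 0.28 × 0.72) / 255) = √(0.3492 / 255) = 0.0370. Power is Φ(0.10 / 0.0370 − 1.960) = 77.1%.

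**3. The same risk difference, standardised over baseline HECSI.** Let x be baseline HECSI in SD units, taken as normal, with logit p_j(x) = a_j + b·x. Choose a_j so that the average response stays at 18% and 28%. The large-sample variance is

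V = E[p₁(1 − p₁)] / 255 + E[p₀(1 − p₀)] / 255 + Var[p₁ − p₀] / 510.

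The SE is 0.0370 × √(variance ratio). The participant equivalent is 510 × (1 − ratio). Results come from unrounded values.

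| Slope b per SD | Variance ratio | SE | Participants | Power |
|---|---|---|---|---|
| 0 | 1.000 | 0.0370 | 0 | 77.1% |
| 0.3 | 0.985 | 0.0367 | 8 | 77.7% |
| 0.5 | 0.959 | 0.0362 | 21 | 78.8% |
| 0.8 | 0.903 | 0.0352 | 49 | 81.1% |

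The gain in power is 0, 0.6, 1.7 and 4.0 percentage points.

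**4. Cross-check at other assumed rates.** Take 25% versus 37% and multiply the variance by (1 − r²), where r is the correlation of baseline HECSI with response. The unadjusted SE is √((0.25 × 0.75 + 0.37 × 0.63) / 255) = 0.0406, with power 84.0%. Power becomes 84.4%, 85.4%, 87.2% and 89.7% at r = 0.1, 0.2, 0.3 and 0.4.

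A simulation around these rates (1,500 trials per scenario) compared the stratified Mantel-Haenszel risk difference with the standardised one. It assumed 20% hyperkeratotic, which is the protocol's cap, and 15% from North America. The efficiency of the standardised estimator relative to Mantel-Haenszel was 1.00 at |r| of 0 and 0.09, 1.04 at 0.17, 1.08 at 0.26 and 1.09 at 0.33. The two mean estimates agreed to within 0.0002 in every scenario (for example 0.1131 and 0.1133), and no precision was lost when baseline HECSI was uninformative.

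**The case against.** The strongest reply is that this is a choice between two valid methods. CMH estimates the stated summary directly, uses exactly the randomisation factors, needs no outcome model, and pools simply over 100 imputations. Bias, type I error and the estimand are not in question. All of this stands. A reader might infer that the plan gives up precision for no gain. The documents do not support that, because simplicity and freedom from a model are real advantages.

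Second, the prognostic premise is not shown. No section reports an association between baseline HECSI and either response. HECSI-90 already divides by own baseline, and restricting entry to IGA-CHE 4 may narrow the spread of HECSI. This also stands, and it is why the range must start at zero.

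Third, the plan's convention is to adjust for the baseline of the measure analysed. For IGA-CHE TS that baseline is constant at 4, so adding baseline HECSI is a new covariate choice rather than a matter of consistency. It would also be wrong to say that the continuous analyses in general adjust for baseline HECSI, since itch and pain use their own scores. The comparison holds for the HECSI change endpoints and, on the natural reading of Section 9.3.6.4, for AUC of HECSI-90.

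The reply does not explain why a baseline value is listed for AUC of HECSI-90 and not for HECSI-90 at Week 12. Nor does it show a loss of precision from adjustment.

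**Conclusion.** The point holds as an optional improvement in efficiency. The CMH analysis is correct as planned. A standardised risk difference that adds baseline HECSI would keep the estimand, need no new data, and not be expected to lose precision.

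At an assumed 18% versus 28% with 510 participants, the gain runs from nothing to about 10% of the variance, or 0 to 4 points of power per test, for log-odds slopes from 0 to 0.8 per SD. The documents do not show where in that range the trial lies. IGA-CHE TS is the likelier of the two to benefit.

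A reader might also infer that the choice of CMH puts the whole confirmatory sequence at risk. The fixed sequence does make any failure costly, but on these assumptions the choice of method moves the chance of failing a test by at most about 4 points.

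The conclusion rests on Section 9 of the protocol, which refers to a SAP for further technical detail. If that SAP already adds baseline HECSI, or explains its absence, the point is closed.

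**What to change.** In Section 9.3.6.3 and the SAP, before database lock:

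- For HECSI-90 and IGA-CHE TS at Week 12, estimate the difference in response rates by standardisation (g-computation) from a logistic model with treatment, region, subtype and baseline HECSI.
- Use a robust or delta-method SE. Where multiple imputation applies, compute the estimate and SE in each dataset and pool by Rubin's rule.
- Do not report the model's odds ratio in place of the risk difference; that would change the effect measure.
- Keep the stratified CMH result as a sensitivity analysis.

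Section 9 allows the SAP to be revised before database lock. Participants and investigators know the treatment, so the covariate should be fixed without reference to outcome data by arm.

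The cost is some SAP wording, program code and reliance on a working outcome model. If the sponsor prefers to keep CMH as the confirmatory analysis, one sentence saying why a baseline value is listed for AUC of HECSI-90 but not used for HECSI-90 at Week 12 would be enough.
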